3.6.2. Outcomes, exposures, and confounders to be measured

Pre-PDC Phase One:

Aim 1: Describe the baseline outcomes of a selected sample of infants discharged from a rural hospital neonatal unit.

1. *Primary Outcome:*

The primary outcome is the proportion of study participants alive with developmental delay.

Developmental delay is defined as one domain that is scored as an area of concern or presence of delay using the Ages and Stages Questionnaire (ASQ-3).

2. *Secondary Outcomes:*

1. Proportion of study subjects deceased
2. Proportion of study subjects with malnutrition
3. Proportion of study subjects with medical co-morbidities, further broken down into the four categories: hydrocephalus, anemia, feeding difficulty, and respiratory disease.
4. Proportion of the study subjects with developmental delay and malnutrition
5. Proportion of study subjects with developmental delay and medical comorbidities

Aim 2: Identify specific patient-level predictors of developmental delay. Main exposures of developmental delay include prematurity, low birth weight and malnutrition. Potential

confounders include but not limited to sector of residence, sex, ubudehe category (measure of economic status), household size, and education level.

Post-PDC Phase Two:

Aim 3: Describe the PDC. This aim is to describe the pediatric development clinic (PDC) after 24 months of implementation in terms of the following main outcomes: services provided, referral system, patient population served and clinical, nutritional, and developmental status after support and follow-up in the clinic.

Other Variables to be measured include (See Appendix F for data source forms)

Characteristics of Clinic Patients

Proportion of study participants per age category and per medical condition.

Broken down by:

- Proportion of infants
- Proportion of children from one year to five years
- Proportion of children born premature
- Proportion of ELBW/ VLBW
- Proportion of infants born at term with HIE or cerebral infection

Proportion of children with developmental delays, trisomy 21, hydrocephalus, cleft lip/palate, and developmental delay

- Proportion of children deceased
- Proportion of children lost to follow-up
- Proportion of children with malnutrition per age category or per medical condition

Clinic activities will be described

Patient flow: Group education, individual social worker screening, clinical evaluation including danger sign assessment, nutritional assessment/classification/treatment, developmental screening/therapy, and condition-specific screening and treatment.

Aim 4: Compare developmental, medical, and nutritional outcomes of children who were enrolled in the PDC to other children on the main outcomes of prevalence of developmental delay as measured using the Ages and Stages Questionnaires (ASQ-3) and the prevalence of undernutrition (stunting, wasting, underweight) using anthropometric assessments.

This aim is to describe the clinical, nutritional, and developmental outcomes of vulnerable patients enrolled in PDC in comparison with:

- a. Medically vulnerable infants who did not receive PDC support. This comparison will be made using a cohort of preterm/LBW children who were born in Rwinkwavu District Hospital (RDH) before PDC started with medical, nutritional and developmental outcomes assessed at 12-36 months of age (the dataset from Aim 1).
- b. The general population of rural Rwandan children.² This comparison will be looking at developmental outcomes of children followed in PDC compared to the similar age children from the general population using UNICEF data that was collected in children ages 0-11 months and 24-35 months randomly sampled from ten rural sectors of the country.

Additional variables to be measured include (See Appendix F for data source forms of routinely collected data and Appendix A for household interview forms. All measures used in the household interview were previously used in the two comparison datasets):

- Descriptive characteristics of caregivers.
- Proportion of visits where a nutritional screening was done, danger sign screening was done, and patient had a documented ASQ within the 6 months prior to visit date.

² This existing data set was collected by UNICEF, Harvard School of Public Health, Partners In Health, and the University of Rwanda. [name] and [name] were investigators on both study teams and have access to the data.

- Proportion of children who received nutrition supplement.
- Proportion of currently enrolled children with a visit in the reference quarter whose caregivers have had at least one documented ECD counseling session
- Proportion of children with moderate or severe chronic malnutrition (height/age Z score < 2 or height/age z score < 3) at the last visit.
- Proportion of children with moderate or severe acute malnutrition (weight/height Z score < 2 or weight/height z score < 3) at the last visit.
- Proportion of children with a completed and documented ASQ in the reference quarter failing one or more domains on the ASQ.
- Mean/median scores on the overall ASQ
- Mortality rate in both groups
- Percentage of patients lost to follow-up
- Opportunities for learning and stimulation in the home, measured by the Rwanda-adapted HOME Inventory and the Rwanda DHS Early Childhood Development Index
- Caregiver mental health, measured by the Hopkin's Symptom Checklist which has been validated in Rwanda and used in Rwanda to assess symptoms of depression and anxiety for over twenty years
- Caregiver-child interactions and discipline practices, using the Kinyarwanda version of the Observations of Mother-Child Interactions (OMCI) as well as the Rwanda DHS Child Discipline Module
- Socioeconomic status of the household, using wealth index from the Rwanda DHS
- Exposure to daily hardships and household stressors

Expanding-PDC Phase Three:

Aim 5: To evaluate the implementation of PDC during expansion, including patient characteristics, provider experiences, quality of care, cost-effectiveness, patient experiences, and patient outcomes. Findings from this aim will be used for continuous quality improvement of the PDC and informing scale-up.

Primary Outcome: The primary outcome is the proportion of study participants alive who are meeting developmental and growth milestones.

Secondary Outcomes:

- Cost-effectiveness of the PDC model
- Adherence to PDC care protocols by PDC providers
- Quality of care
- Enrollment rates, clinic retention, and barriers to care
- Patient and provider experiences
- Impact of training and mentorship in the PDC protocol
- Evaluation of improved exclusive breastfeeding prior to PDC referral
- Impact of PDC mHealth tool on protocol adherence and child growth
- Impact of PDC on child outcomes in Kirehe

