3.2. Study design

Pre-PDC Phase One:

The first phase is a **cross-sectional study** of infants discharged from a district hospital unit using caregiver report of medical and developmental outcomes as well as relying on measured growth parameters for nutritional status. This study will serve as a baseline of developmental, medical, and nutritional outcomes for comparison to similar children who received services from the PDC.

Post-PDC Phase Two:

All under 5 years of age, high risk (preterm, LBW) children enrolled in PDC since April, 2014 when PDC was initiated. The second phase will be a second cross-section of children who have been receiving services from the PDC from April 2014 when the clinic launched until present. The study will describe PDC implementation, demographic characteristics, and clinical, nutritional and developmental outcomes of all children from zero to five years of age enrolled in PDC from April 2014 to the time of study.

Post-PDC Phase Three:

This phase will use mixed methods, with data sources including routinely collected data, chart review, household data collection, focus groups and interviews to evaluate the PDC as it expands to new areas. The study will provide essential information of the feasibility of the PDC model at larger scale. The study will describe barriers to care, retention, long-term patient outcomes, and provider and patient experiences, quality of care delivered in the PDC especially on growth monitoring and developmental screening and costing of the PDC.

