3.5. Selection of study population

3.5.1. Inclusion criteria

Baseline Phase One:

All infants discharged from Rwinkwavu hospital neonatal unit and born at less than 37 weeks and infants born less than 2 kilograms during the designated study period.

Post-PDC Phase Two:

All children under five years of age enrolled in PDC in Rwinkwavu District Hospital catchment area PDC clinics, will be included in Aim 3 and Aim 4b. Aim 4a will include only preterm and/or LBW (<2000g) infants for comparison with the baseline population of similar infants.

Expanding-PDC Phase Three:

All children under five years of age and their caregivers referred to or enrolled in PDC in Rwinkwavu and Kirehe District Hospital catchment areas. In addition, newborns and their caregivers from Rwinkwavu and Kirehe District Hospital catchment areas will be included as the primary referral patient population to PDC. PDC providers will also be included in some components of the evaluation.

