3.5.5. Proposed Intervention

Children in Phases Two and Three of this study have participated in the PDC program as described previously, unless they are in a comparison group. The PDC provides medical, nutritional and developmental supportive programs to at-risk children under age five using trained nurses and social workers in addition to overall clinic supervision by a general practitioner. Children are referred to the PDC from the hospital (neonatal unit, maternity, inpatient pediatrics, and the outpatient or emergency departments), health centers, and from the community. Children are eligible to enroll in the PDC if they meet the following program eligibility criteria: prematurity, low birth weight (<2000grams), hypoxic ischemic encephalopathy, hydrocephalus, cleft lip and palate, trisomy 21, post central nervous system infections (meningitis and cerebral malaria) severely malnourished children requiring hospitalization post-discharge, as well as children presenting with other developmental delays. Children come in for routine visits, on a timeline determined by their specific condition. On each PDC clinic day, social workers facilitate a group counseling session focused on topics relevant to children's growth and development. After group sessions, children undergo a clinical screening and growth monitoring by a nurse as well as one-on-one sessions with a social worker to identify needs for additional social support whether financial, emotional, nutritional, or a home visit. PDC social support groups are formed to engage father's in the care of their children. Health

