Appendix A: Household Data Collection Tools

Previously Approved tools include:

- Informed Consent form for study Aim 4
- Early Childhood Development Survey for study Aim 4

New tools include:

- Informed consent form for study Aim 5
- Developmental screening tools for study Aim 5

Appendix B: New Tools Phase 3

New tools include:

- New/revised medical record forms for the PDC
- Neonatal Unit Register
- Breastfeeding quality improvement project data tracker
- Guide for Monitoring Child Development
- Qualitative interview guides and consents

[Appendix C: CVs of New Investigators](#)

- [name], Partners In Health
- [name], MD, Boston Children's Hospital Global Pediatrics Fellow
- [name], Partners In Health

[Appendix D: Prior RNEC Approvals](#)

Approved by Rwanda National Ethics Committee, 9 September 2017

[Appendix E: Payment Receipt for August RNEC Review](#)

[Appendix F: Previously Approved Study Tools](#)

Previously approved study tools that are still in use in the PDC program are included here. These include routine Pediatric Development Clinic Medical Record forms, a mentorship checklist, and the Ages and Stages Questionnaires administered starting at age 6 months in the clinic.

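### The Aim 4 visit variable needs an ASQ in the previous 6 months at visits of any age, but the clinic starts the ASQ at 6 months, so earlier visits fail automatically

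*Combined protocol and SAP*

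**What the plan says.** Section 3.6.2, under Aim 4, lists additional variables to be measured. One is visit-based: "Proportion of visits where a nutritional screening was done, danger sign screening was done, and patient had a documented ASQ". The ASQ condition in full is that the "patient had a documented ASQ within the 6 months prior to visit date". No lower age is set and no visits are exempted.

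The note under Appendix F describes the tools still in use in the programme, among them the "Ages and Stages Questionnaires administered starting at age 6 months in the clinic". It does not say whether this age is chronological or adjusted for prematurity.

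Three places show that the clinic population includes infants younger than that:

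- Section 3.2 describes Phase Two as covering "outcomes of all children from zero to five years of age enrolled in PDC".
- Section 3.5.1 sets no lower age for Aims 3 and 4b: "All children under five years of age enrolled in PDC in Rwinkwavu District Hospital catchment area PDC clinics".
- Section 3.5.5 gives the referral routes: "Children are referred to the PDC from the hospital (neonatal unit, maternity, inpatient pediatrics" and others.

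The visit schedule is described only in general terms: "Children come in for routine visits, on a timeline determined by their specific condition".

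**The concern.** The variable reads as a measure of how completely the clinic screens its patients. As worded, it also depends on how old the patients are. A visit at 2 or 4 months with nutritional and danger-sign screening both done is scored as a miss, because the clinic does not give an ASQ at that age. The reported proportion would understate adherence by an amount set by the age mix of visits. Two sets of visits with identical care but different age mixes would give different values. A reader of the Aim 4 results could take the shortfall for missed screening.

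**Working it through.** The documents give no value, target or sample size for this variable, so there is no figure to reproduce. The check is of the definition, followed by simple arithmetic.

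**Inputs from the documents**

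- Unit of analysis: the visit (Section 3.6.2, Aim 4).
- Look-back for the ASQ: 6 months before the visit (same place).
- Age at which the clinic starts the ASQ: 6 months (Appendix F).
- Age at entry: from zero, with referral from the neonatal unit and maternity (Sections 3.2 and 3.5.5).
- Share of visits before 6 months: not given.

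**Step 1: can an early visit pass?** A child seen before 6 months has had no clinic ASQ. The ASQ given at the Aim 4 household interview does not help, because those children enrolled at least 12 months before data collection (Sections 3.5.3 and 3.6.1) and so are at least 12 months old at interview. The chance of meeting the ASQ condition at such a visit is therefore 0 by design.

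**Step 2: ceiling.** Let s be the share of visits before 6 months and q the true adherence at all other visits.

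Reported value = (1 − s) × q. Maximum, at q = 1, is 1 − s.

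| Assumed s | Maximum | Reported value if q = 90% |
|---|---|---|
| 10% | 90% | 81% |
| 20% | 80% | 72% |
| 30% | 70% | 63% |
| 40% | 60% | 54% |
| 50% | 50% | 45% |

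**Step 3: what s might look like.** The two schedules below are invented for illustration. Both start at age 1 month, assume full adherence, count an ASQ done at the 6-month visit itself, and assume ASQs are repeated often enough that every later visit has one in its window. In each, 5 visits (months 1 to 5) fall before 6 months.

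| Follow-up to age | Monthly visits | Monthly to 6 months, then every 3 months |
|---|---|---|
| 12 months | 7/12 = 58.3% | 3/8 = 37.5% |
| 24 months | 19/24 = 79.2% | 7/12 = 58.3% |
| 36 months | 31/36 = 86.1% | 11/16 = 68.8% |

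**Step 4: same-day ASQs.** If the wording excludes an ASQ done on the visit date, the 6-month visit also fails. The 24-month ceilings become 18/24 = 75.0% and 6/12 = 50.0%. On that reading a child's first clinic visit also fails at any age, since no earlier clinic ASQ exists.

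**Step 5: does the reading of the list matter?** If the three items are meant as three separate proportions, the two other screenings are unaffected and the ceiling applies to the ASQ proportion alone. The fault remains in that part.

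**The case against.** The strongest reply has three parts.

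First, status. This is one of many additional variables. The main Aim 4 outcomes are the prevalence of developmental delay and of undernutrition, and the Aim 4 analysis plan in Section 3.6.4 neither tests this variable nor compares it between clinics or over time. That is right, and it limits the weight of the point.

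Second, the denominator may be narrower than it looks. The household sample enrolled at least 12 months earlier, and neighbouring variables use a reference quarter or the last visit. If only recent visits of that sample were counted, none would be before 6 months. But the enrolment rule selects children for interview and does not remove their earlier clinic visits. Section 3.5.6 draws routine data from all enrolled children, and this variable carries no time limit although its neighbours do. As written, early visits are in.

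Third, reach. A reader might infer that the fault distorts Phase Three: that new Kirehe clinics would look worse than established ones, or that a cohort growing older would pass for an effect of mentorship or the mHealth tool. Phase Three does study "quality of care delivered in the PDC especially on growth monitoring and developmental screening", and protocol adherence is a secondary outcome of Aim 5. But no section says this variable is used there. Section 3.6.4 refers to defined standards, Section 3.5.5 describes observation checklists, and Appendix A lists new developmental screening tools for Aim 5. The documents also do not say that Kirehe clinics would enrol mainly newborns. This part of the reply stands in full.

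Timing also counts. Section 6.2 ends Phase Two in March to May 2016, while the text was approved in September 2017. For Aim 4 the change may therefore be one of computation and reporting only.

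**Conclusion.** The point holds for the variable as defined. Visits before 6 months fail the ASQ condition whatever the quality of care, and the maximum is 1 minus their share of all visits. This follows from the text of Section 3.6.2 and Appendix F, and needs only that some counted visits fall before 6 months.

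The size cannot be determined. Ceilings of 80% and 60% correspond to assumed shares of 20% and 40%, and the schedules in the working are likewise illustrative. No large shift between clinics or over time should be claimed, because any such figure would rest on shares that the documents do not supply. If the clinic's starting age is an adjusted age, preterm infants stay ineligible for longer after birth and the ceiling is lower.

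The consequence is confined to one descriptive Phase Two variable. The main Aim 4 comparisons do not depend on it.

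**What to change.** Amend the definition in Section 3.6.2:

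1. Score the ASQ condition only at visits at or after the age at which the clinic starts the ASQ, and state whether that age is chronological or adjusted, matching clinic practice.
2. State that an ASQ completed on the visit date counts.
3. Report nutritional screening and danger-sign screening as separate proportions over all visits. If a combined figure is kept, limit it to visits eligible for the ASQ.
4. If the variable is reused under Aim 5, apply the same denominators there.

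With the ASQ condition limited in this way, the ceiling returns to 100% and the proportion estimates q directly.

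The cost is a few lines of wording and no new data collection. The documents do not list date of birth as a record field, but height-for-age z-scores (Section 3.6.2) and age-specific ASQ forms (Section 3.6.1) already require the child's age. The downsides are a smaller denominator for the ASQ element and, if adjusted age is used, some misclassification near the threshold, since Section 4 notes that gestational and adjusted age are error-prone.

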3.4. Study population

Pre-PDC Phase One:

All infants discharged from the Rwinkwavu District Hospital neonatal unit during the designated time period fulfilling the inclusion criteria: children were included if they were discharged between October 2011-October 2013 (prior to PDC implementation).

Post-PDC Phase Two:

All children enrolled in the PDC are eligible. PDC serves children up to age five years with prematurity, low birth weight, birth asphyxia, other perinatal risks, and other developmental delays.

Expanding-PDC Phase Three:

All children and their caregivers enrolled in the PDC clinics in S. Kayonza and Kirehe Districts are eligible. PDC serves children up to age five years with prematurity, low birth weight, birth asphyxia, other perinatal risks such as post CNS infections_cerebral malaria and meningitis, and other developmental delays.

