3.5.3 Sampling

Pre-PDC Phase One:

Potential participants will be identified and sampling will be conducted in the following manner. The study coordinator will use the Rwinkwavu neonatal registry after obtaining consent from the medical director to identify potential study participants based on the inclusion criteria outlined above. The following identifiers will be extracted from the registry: name, sex, date of birth, discharge date and mother's name. After the identification of potential participants, the patient files will be located and examined to compile the demographic information of the infants: sector, cell, village, and health center.

Post-PDC Phase Two:

All children enrolled in the PDC are eligible and no new data will be collected for Aim 3. Children will be identified through PDC patient records, which include patient registers, patient enrollment forms, routine program forms, and the electronic medical record (EMR). To complete Aim 4, additional assessments of children's growth, development, and home environment including parenting practices will be conducted through household interviews with the primary

caregivers of PDC patients. Patient names and household location will be extracted from the EMR of patients who enrolled in the PDC at least 12 months prior to data collection.

Expanding-PDC Phase Three:

All children enrolled in the neonatal units or PDC, their caregivers, and PDC providers are eligible for participation in this aim. Children will be identified through neonatal unit and PDC patient records, which include patient registers/charts, patient enrollment forms, routine program forms, and the electronic medical record (EMR).

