The majority of phase two data comes from existing program records, both paper-based and electronic as well as pre-existing de-identified data. The procedure is as follows for using routinely collected program data: After RNEC and MOH approvals are obtained, data will be collected from electronic medical records (EMR) and paper forms that are part of routine programmatic record keeping (See Appendix F for complete list of PDC routine data collection forms approved; new routine forms are contained in Appendix B). Demographic characteristics, anthropometric measurements, clinical, nutritional and developmental outcomes information will be extracted from the PDC EMR dataset and patient files. After extraction from the original dataset, data will be transferred into STATA (Stata Corp, College station, Texas, USA) for data cleaning and further statistical analysis. Patient identifiers will be removed and unique identification numbers will be assigned to the working dataset to respect patient confidentiality. As Aim 3 is a secondary dataset analysis of de-identified patient records, no individual patient consent procedure will be needed.

Aim 4 will include household interviews with caregivers of children who enrolled in PDC at least 12 months prior to data collection (see study tools for household data collection in Appendix A). These patients will be identified using EMR records and will be asked if they are willing to be contacted by the study team by PDC staff. If a caregiver is willing to participate, he/she will be contacted by the study team and complete informed consent prior to data collection. Consenting participants will complete an interview about the child's development, nutrition, parenting, and the home environment (see Appendix A for household data collection tool). Child development will be measured using the Ages and Stages Questionnaire, as has been previously approved for use in this study protocol. Appendix A contains all 20 age-specific forms of the Ages and Stages Questionnaires, however each caregiver will be asked only the 30 age-specific questions that are appropriate for their child; all questions for children of different ages will be skipped. Data will be collected on Android tablets using the software platform

KoboCollect.

Expanding-PDC Phase Three:

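### In Aim 4a, deaths between neonatal-unit discharge and PDC enrolment can count in the baseline group but never in the PDC group, so the two mortality rates are not comparable

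*Combined protocol and SAP*

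**What the plan says.** **Baseline group.** Section 3.4 defines it as "All infants discharged from the Rwinkwavu District Hospital neonatal unit during the designated time period fulfilling the inclusion criteria", with discharge between October 2011 and October 2013. Section 3.5.3 draws the list from the neonatal registry. Section 3.6.2 includes "Proportion of study subjects deceased" among the Phase One secondary outcomes, so deaths after discharge are meant to be counted.

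**PDC group.** Section 3.4 says "All children enrolled in the PDC are eligible", and section 3.5.3 says "Children will be identified through PDC patient records". For the Aim 4 household interviews, section 3.5.3 takes "patients who enrolled in the PDC at least 12 months prior to data collection"; sections 3.5.7 and 3.6.1 use the same condition. Section 3.5.6 instead describes children who have attended the clinic for a year or longer.

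**Comparison.** Section 3.6.2 lists "Mortality rate in both groups" as an additional Aim 4 variable. For Aim 4a, the groups are aligned on preterm/low-birth-weight status (3.5.1) and on exclusions (3.5.2) only. Section 3.6.4 plans chi-square or Fisher tests for developmental, nutritional and medical outcomes. It does not name mortality and mentions neither a landmark nor delayed entry. The Phase Two limitations in section 4 do not raise the issue.

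**The concern.** A child can appear in PDC records only after surviving to enrolment. A baseline child appears in the registry from discharge, whatever happens next. This is left truncation in one group only. If any deaths fall between discharge and enrolment, and nothing offsets this, a programme with no effect on survival would show lower mortality than the baseline.

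The gap need not be short. Section 3.5.5 allows referral from outpatient departments, health centers and the community as well as from the neonatal unit. The clinic takes children up to age five and opened in April 2014, and Aim 4a sets no limit on birth date or age at enrolment. A preterm child discharged in 2012 could therefore enrol in 2014, having already survived the interval.

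Follow-up length also differs. Baseline status is taken at 12-36 months of age. PDC status is taken at a time set by the enrolment date. A crude proportion deceased in each group mixes these horizons.

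**Working it through.** The documents give no mortality rate, enrolment delay or sample size for this comparison, so there is no planned figure to reproduce. The check has two parts.

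**1. Who can be counted**

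| Event | Baseline | PDC |
|---|---|---|
| Death after discharge, before the point of PDC enrolment | can count (3.4, 3.5.3, 3.6.2) | cannot count: no PDC record exists (3.5.3) |
| Death after PDC enrolment | no equivalent entry point; counted from discharge | can count, from the EMR or other patient records (3.6.3) |

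**2. Illustrative size (assumed inputs)**

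Let M be the true post-discharge mortality to a common horizon, equal in both groups, and s the share of those deaths that precede PDC enrolment. The baseline shows M. The PDC group, conditional on survival to enrolment, shows M(1−s)/(1−Ms). The apparent risk ratio is (1−s)/(1−Ms).

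With M = 8%:

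| s | PDC mortality | Risk ratio |
|---|---|---|
| 0% | 0.080/1.000 = 8.0% | 1.00 |
| 10% | 0.072/0.992 = 7.3% | 0.91 |
| 20% | 0.064/0.984 = 6.5% | 0.81 |
| 50% | 0.040/0.960 = 4.2% | 0.52 |

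The choice of M matters little. At s = 50%, M = 5% gives 0.5/0.975 = 0.51 and M = 15% gives 0.5/0.925 = 0.54. The result is driven by s, which is unknown.

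**Effect of the section 3.5.6 wording.** If the denominator is children who have already attended for a year, s becomes the share of deaths before that point. Assuming 70% or 90%, with M = 8%, the ratio is 0.3/0.944 = 0.32 or 0.1/0.928 = 0.11. An enrolment-date condition, as in sections 3.5.3, 3.5.7 and 3.6.1, does not by itself require a year's survival.

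**Opposing error.** Suppose a share u of baseline deaths is lost because those families refuse or cannot be traced, and these children leave the denominator too. The baseline then shows M(1−u)/(1−Mu). With u = s the two errors cancel: at 20% each, both groups show 6.5% and the ratio is 1.00. The direction of the truncation is therefore known, but the net direction is not.

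**The case against.** Several stronger readings are tempting, and the documents do not support them.

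- **All early deaths at home count only against the baseline.** A reader might infer this, but only deaths before enrolment are lost. A death soon after prompt enrolment can be in PDC records. The gap is stated nowhere, and if every child enrolled at discharge this bias would be zero.
- **The whole of Aim 4 is affected.** Section 3.6.4 says the Aim 4b dataset holds only demographics and current developmental and nutritional status, so the point concerns Aim 4a alone.
- **Differences in finding deaths add to the advantage.** In Phase Two, caregivers "will be asked if they are willing to be contacted by the study team by PDC staff", and deaths after loss to follow-up may stay unknown. But that step governs the household interviews, and Aim 4 data also come from the EMR. Phase One excludes families who decline (3.5.2) and reaches homes through community health workers (3.5.6), so baseline deaths can be missed too. This could push either way.
- **The plan will claim better survival.** It says no such thing. Mortality is an additional variable, no mortality test is named, and section 4 disclaims causality. The figures of 8% and 10-50% are assumptions.

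All of this limits the point's scope and size. It does not remove the mismatch. The general caveat about causality does not tell a reader that one group's pre-enrolment deaths are absent by construction. Loss to follow-up is listed next to mortality, but that covers only children who had already enrolled.

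**Conclusion.** The concern holds for Aim 4a. The two cohort definitions give different entry points, and nothing in the plan corrects for this before the two mortality figures are set side by side. Taken alone, the truncation favours PDC whenever any death falls between discharge and enrolment. Its size cannot be computed from the documents. Under an assumed 8% mortality, equal horizons and complete recording of all other deaths, the apparent risk ratio runs from 1.00 to 0.52 as the share of deaths before enrolment runs from 0% to 50%. It would be further from 1 if section 3.5.6 defines the denominator. Incomplete recording of deaths in either group, and unequal follow-up, leave the net bias uncertain. Because mortality is not a main Aim 4 outcome, this should be corrected but does not undermine the main developmental and nutritional comparisons.

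**What to change.** 1. In section 3.6.2, limit the mortality comparison to Aim 4a and to PDC children who were discharged from the neonatal unit and meet the Aim 4a criteria. A clock starting at discharge is undefined for children never admitted there.
2. Use all such enrolled children as the denominator, not only those interviewed. Reconcile section 3.5.6 with sections 3.5.3, 3.5.7 and 3.6.1.
3. Check whether Phase One recorded date or age at death. Section 3.6.4 lists only alive/dead, and the registry fields in section 3.5.3 include no death date.
   - **If recorded:** compare on time since discharge to a common horizon, with PDC children entering at enrolment (delayed entry). Alternatively, start both groups at a common landmark, keeping only children alive at that point and, for PDC, already enrolled. Show the result with children of unknown status in either group counted as all alive and as all dead.
   - **If not recorded:** make no between-group mortality comparison. Report the two figures separately and state that they are not comparable because deaths before enrolment are absent from the PDC group.
4. Add that statement to the Phase Two limitations in section 4 in the second case.

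The cost is plan wording and the use of discharge, enrolment and death dates where they exist; no new participants or visits are needed. The downside is that early baseline deaths leave the comparison, or the comparison is dropped, so the result will look less favourable to PDC.
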